8.2 Radiology Studies

8.2.1 Central Radiology Review for Response:

Patients who respond (CR, PR) to therapy or have long term stable disease (SD) (≥ 6 cycles) on protocol therapy will be centrally reviewed. The Operations center will notify the site when a patient has met the criteria for review. The tumor disease evaluations to be submitted for review include baseline (pre-study) evaluations as well as all end of cycle tumor disease evaluations which occurred while the patient was on the subprotocol therapy study.

8.2.2 Technical Details of Submission:

To ensure an adequate interpretation of FDG-PET and CT with contrast scans, scans transferred between the treating institutions and the Imaging and Radiation Oncology Core Group IROC RI (QARC) must be submitted in Digital Imaging and Communications in Medicine (DICOM) format. BMP files, JPG files, or hard copies (films) are unacceptable for adequate interpretation of PET and CT with contrast scans. Imaging studies must be submitted electronically as outlined in the following paragraph. The images will be made available to study radiologists and nuclear medicine physicians for central review.

Submission of Diagnostic Imaging data in DICOM format is required. Submission of the digital files and reports via TRIAD is preferred. Instructions for TRIAD set up are below.

Alternatively, the images and reports may be submitted via sFTP to IROC Rhode Island. Digital data submission instructions including instructions for obtaining a sFTP account, can be found at <http://irocri.qarc.org>. Follow the link labeled digital data. Sites using the Dicommunicator software to submit imaging may continue to use that application.

Corresponding Radiology reports may be submitted along with the electronic submission via TRIAD or sFTP or may be emailed to [contact]. The COG operations center and IROC are available to assist with any queries regarding the corresponding radiology reports which should be included when the scans are submitted

Questions may be directed to [contact] or [contact].

Digital RT Data Submission Using TRIAD (if TRIAD is available at your site):
TRIAD is the American College of Radiology's (ACR) image exchange application. TRIAD provides sites participating in clinical trials a secure method to transmit DICOM and DICOM RT files and other digital objects, such as reports. TRIAD de-identifies and validates the images as they are transferred.

TRIAD Access Requirements:

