10.0 CRITERIA FOR REMOVAL FROM PROTOCOL THERAPY AND OFF STUDY CRITERIA

10.1 Criteria for Removal from Protocol Therapy

- a) Clinical (including physical examination or serum tumor markers) or radiographic evidence of progressive disease (See [Section 12](#)).
- b) Adverse Events requiring removal from protocol therapy (See [Section 6](#)).
- c) Refusal of protocol therapy by patient/parent/guardian
- d) Non-compliance that in the opinion of the investigator does not allow for ongoing participation.
- e) Completion of 26 cycles of therapy.
- f) Physician determines it is not in the patient's best interest.
- g) Repeated eligibility laboratory studies (CBC with differential, bilirubin, ALT (SGPT) or serum creatinine) are outside the parameters required for eligibility prior to the start of protocol therapy (See [Section 8.1](#)).
- h) Study is terminated by Sponsor.

- i) Pregnancy
- j) Patient did not receive protocol treatment after study enrollment

Patients who are removed from protocol therapy during cycle 1 should continue to have the required observations in [Section 8.1](#) until the originally planned end of the cycle or until all adverse events have resolved per [Section 13.4.4](#), whichever happens LATER. The only exception is with documentation of the patient's withdrawal of consent from the APEC1621SC screening protocol. Patients who are removed from protocol therapy in subsequent cycles should have the necessary observations to ensure adequate clinical care.

10.2 **Follow-Up Data Submission and APEC1621SC Off Study Criteria**

Patients who are off subprotocol therapy will initially be followed on the therapeutic subprotocol for a 30-day period. During follow-up on the therapeutic subprotocol ongoing adverse events, or adverse events that emerge after the patient is removed from protocol therapy, but within 30 days of the last dose of investigational agent, must be followed and reported via RAVE and CTEP-AERS (if applicable). Upon completion of subprotocol follow-up period, the patient will continue to be followed on the APEC1621SC screening protocol. Follow-up data submission will occur until one of the APEC1621SC Off Study Criteria is met (See Section 10 of APEC1621SC for details); consent is withdrawn or the patient dies or is lost to follow-up.

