evaluation period for determination of best response will be 6 treatment cycles. All other patients will be considered non-responders. Patients who are not evaluable for response evaluation may be replaced for the purposes of the statistical rule. All patients considered to have a response (CR or PR) must have imaging studies reviewed centrally at the COG. Centers will be notified by the COG about requests for scans of patients with stable disease. Preliminary assessment of activity using institutionally provided tumor measurements will be entered into CDUS quarterly. The central review by COG will be provided as the final reviewed assessment of response when such becomes available.

11.6 **Evaluability for Toxicity**

All eligible patients who receive at least one dose of protocol therapy will be considered in the evaluation of toxicity.

11.7 **Progression free survival (PFS)**

Progression free survival will be defined as time from the initiation of protocol treatment to the occurrence of any of the following events: disease progression or disease recurrence or death from any cause. All patients surviving at the time of analyses without events will be censored at their last follow-up date.

PFS along with the confidence intervals will be estimated using the Kaplan-Meier method. Patients with local calls of disease progression (i.e. calls made by the treating institution), will be counted as having had an event, even if the central review does not declare progression. We will also report PFS based on central radiology review as a secondary analysis, if adequate number of disagreements in progressions exist between the treating institutions and the central radiology review to make such an analysis meaningful.

11.8 **Correlative Studies**

A descriptive analysis of the exploratory aims described in [Section 1.3](#) will be performed and will be summarized with simple summary statistics. All of these analyses will be descriptive in nature.

11.9 **Gender and Minority Accrual Estimates**

The gender and minority distribution of the study population is expected to be:

Racial category	Ethnicity					
	Not Hispanic or Latino		Hispanic or Latino			
	Female	Male	Female	Male		
American Indian/Alaska Native	0	0	0	0	0	
Asian	1	1	0	0	2	
Native Hawaiian or Other Pacific Islander	0	0	0	0	0	
Black or African American	3	5	0	0	8	
White	12	20	3	2	37	
More than one race	1	0	1	0	2	
Total	17	26	4	2	49	

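### PFS is censored at last follow-up without requiring that progression status was known then, and the conditional central-review PFS relies on reads that the planned review does not cover

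*Combined protocol and SAP*

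**What the plan says.** PFS is the first secondary aim (1.2.1), estimated by Kaplan-Meier in a single-arm study. Section 11.7 counts progression, recurrence and death from any cause as events and lets the treating institution's progression call govern. For everyone else it says: "All patients surviving at the time of analyses without events will be censored at their last follow-up date". Section 12.2 repeats the definition and adds no censoring rule.

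The table in 8.1 places tumor evaluations at every other cycle three times, then every third cycle. After therapy, 10.1 and 10.2 say:

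- "Patients who are removed from protocol therapy in subsequent cycles should have the necessary observations to ensure adequate clinical care"
- "Patients who are off subprotocol therapy will initially be followed on the therapeutic subprotocol for a 30-day period", a period described in terms of adverse events
- after that, "the patient will continue to be followed on the APEC1621SC screening protocol"

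On central review, 11.7 says: "We will also report PFS based on central radiology review as a secondary analysis, if adequate number of disagreements in progressions exist". The selection rule in 8.2.1 is: "Patients who respond (CR, PR) to therapy or have long term stable disease (SD) (≥ 6 cycles) on protocol therapy will be centrally reviewed". For those patients the submission is the baseline evaluation plus "all end of cycle tumor disease evaluations which occurred while the patient was on the subprotocol therapy study". Section 11.5 adds: "Centers will be notified by the COG about requests for scans of patients with stable disease". Footnote 7 to the 8.1 table lets the investigator call progression in a solid-tumor patient on clinical or laboratory grounds without imaging.

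**The concern.** **(a) Censoring date.** Section 10.1 allows several exits from therapy without progression: adverse events, refusal, non-compliance, physician decision, or completing 26 cycles. A patient who leaves in one of these ways can be contacted and known to be alive while nobody has recorded whether the tumor has progressed. Under 11.7 that patient stays in the risk set as progression-free until the contact date. Any resulting error is upward, and a single-arm study has no comparator to share it.

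**(b) Central-review PFS.** Whether this analysis appears depends on how many disagreements are seen, on a threshold that is not stated. Disagreement can be seen only where a central read exists. The review rules select on response or long stable disease, so a patient whose first outcome is early local progression is not selected. Section 11.7 does not say how such patients would enter a central-review curve.

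**Working it through.** The documents give no PFS target, event count or drop-off rate, so there is no plan figure to reproduce. Part (a) compares the text and then sizes the error under assumptions. Part (b) is a text comparison with one short calculation.

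**(a) Text.**
- 11.7: censor at last follow-up.
- 8.1: disease evaluations tied to treatment cycles.
- 10.1: after removal in later cycles, only what clinical care needs.
- 10.2: 30 days on this subprotocol, then APEC1621SC.
- 12.4.3: asks for progression to be documented after treatment stops, but in a note on symptomatic deterioration only.
- 14.1: points to a separate CRF packet.

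Neither APEC1621SC nor the CRF packet is among these documents. Last follow-up can therefore fall after the last date on which the patient was known to be progression-free.

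**(a) Size.** Every input is an assumption:
- exponential time to progression, median 4, 6 or 9 months (true 12-month PFS 12.5%, 25.0%, 39.7%)
- 2% or 4% per month leaving therapy without progression, capped at 26 cycles
- median survival after progression 3, 6 or 12 months, with deaths counted as events
- last contact 18 to 48 months after start
- off-therapy progression status recorded in 100%, 75%, 50% or 0% of patients
- progression dated exactly

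Error of the rule in 11.7 in simulated 12-month Kaplan-Meier PFS, in percentage points:

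| Status captured off therapy | 4%/month leaving | 2%/month leaving |
|---|---|---|
| 100% | 0 | 0 |
| 75% | +1.0 to +2.2 | +0.5 to +1.3 |
| 50% | +2.1 to +4.6 | +1.1 to +2.5 |
| 0% | +4.2 to +9.1 | +2.3 to +5.0 |

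A re-run with separate code agreed to within a few tenths of a point.

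Random error for comparison, at 25% PFS: 1.96 × √(0.25 × 0.75 / 20) = 0.19, or 19 points. With 41 patients (20 + 21 expansion) it is 1.96 × √(0.25 × 0.75 / 41) = 0.13, or 13 points.

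**(a) What a better rule achieves.** Example: median PFS 6 months, median post-progression survival 6 months, 50% capture, 4% per month leaving. The present rule is off by +3.5 points. Censoring at the last documented progression-free date, with all deaths as events, is off by +2.3. So 2.3 / 3.5 = 66% of the error remains. It remains because, in patients with unrecorded status, a later death is still counted, at the death date and not at the earlier progression.

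**(b) Text.** Selected for central review: CR, PR and stable disease of at least 6 cycles (8.2.1), plus stable-disease scans on request (11.5). Not selected: local progression before 6 cycles with no earlier response. Some solid-tumor progressions will have no scan to read.

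**(b) Size.** Six cycles are 168 days, or 5.52 months. With exponential PFS, S(168 days) = 2^(−5.52 / median), which is 0.384, 0.529 and 0.654 for medians 4, 6 and 9 months. The share with no required central read is (1 − S) × (1 − response rate). This uses the design's response rates of 5% and 25% and assumes that response is unrelated to early progression:

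- median 4: 0.616 × 0.95 = 0.585; 0.616 × 0.75 = 0.462
- median 6: 0.471 × 0.95 = 0.447; 0.471 × 0.75 = 0.353
- median 9: 0.346 × 0.95 = 0.329; 0.346 × 0.75 = 0.260

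The range is about 26 to 58%, or roughly 5 to 12 of 20 patients. If responders tend to progress later than others, the share would be higher.

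**The case against.** The strongest reply to (a) is that the answer lies in documents not seen here. APEC1621SC follow-up and the CRF packet may record progression at every contact. Section 11.7 does not restrict local progression calls to those made on therapy, and it counts any death. Only patients who leave without progression are exposed. All of this stands: a reader might infer that PFS will be overstated, but the documents support only that it will be if capture is incomplete. What survives is that the rule relies on a condition it does not state.

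It is also fair that the replacement rule is a partial remedy, and that the error is below random error. Both stand, though more patients would not shrink a systematic error.

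A reader might further infer that two versions of the new rule, one counting all deaths and one censoring deaths long after the last documented status, would bracket the true value. They do so in the simulation only because progression is dated exactly. If on-therapy progression is dated at the next scheduled scan, every version shifts up. With median post-progression survival of 6 months and 4% per month leaving, the error at full capture is already +1.3 to +1.7 points. In the 50%-capture example the late-death version moves from −1.0 to about +1, so both versions lie above the truth. No bracketing should be claimed.

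On (b), a reader might infer that no disagreement about early progression can be counted. That goes too far. Responders and long-stable patients have all their on-therapy scans submitted, so a central call of progression at cycle 2 or 4 against a local call of response or stable disease is visible. Section 12.5.3 also has MIBG response in neuroblastoma assessed centrally. The blind spot is early local progression without a prior response. Finally, local calls govern the main PFS, so (b) touches only an optional analysis.

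**Conclusion.** Both parts hold in limited form, and the point is minor.

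(a) The censoring rule in 11.7 can overstate PFS for patients who leave therapy without progression, in proportion to how much later progression goes unrecorded. On the stated assumptions at 4% per month the 12-month error is about +1 to +2 points at 75% capture, +2 to +5 at 50% and +4 to +9 at none. It is zero at full capture. Actual capture cannot be determined from these documents.

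(b) The trigger for the central-review PFS is unquantified, and the disagreements that the planned review can show come from patients largely selected on response or long stable disease. A central-review PFS for the whole cohort is not supported; a comparison within the reviewed subset is. The 26 to 58% without a required read rests on assumed exponential PFS and the design's response rates.

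The response-rate decision rule and the expansion cohorts are unaffected.

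**What to change.** **(a)** Reword 11.7 so that patients without an event are censored at the last date they were documented to be progression-free. That date is a disease evaluation or a contact that records progression status, or the start of treatment if there is neither. Keep death from any cause as an event at its date. Show last-follow-up censoring as a sensitivity analysis and report how many patients' last contact had no recorded status. An analysis censoring late deaths is optional and should not be presented as the other end of a bracket.

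**(b)** Remove the data-dependent trigger, drop the whole-cohort central-review PFS, and report local-central concordance on progression in the reviewed subset, with the number reviewed.

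**Cost.** Wording in 11.7, one sensitivity run and one concordance table; no added scans or readers. Follow-up may be clearly shorter for patients with unrecorded status, because their censoring date moves back to the last documented evaluation. The sponsor should confirm whether APEC1621SC follow-up and the CRF packet record progression status at each contact. If they always do, the new censoring rule changes nothing.

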12.0 EVALUATION CRITERIA

12.1 Common Terminology Criteria for Adverse Events (CTCAE)

The descriptions and grading scales found in the current version of the NCI Common Terminology Criteria for Adverse Events (CTCAE) version 5.0 will be utilized for AE reporting. All appropriate treatment areas should have access to a copy of the current CTCAE version 5.0. A copy of the CTCAE version 5.0 can be downloaded from the CTEP website (<http://ctep.cancer.gov>).

12.2 Progression-Free Survival

Progression-free survival (PFS) is defined as the duration of time from start of subprotocol treatment to time of progression or death, whichever occurs first.

Development of new disease or progression in any established lesions is considered progressive disease, regardless of response in other lesions – e.g., when multiple lesions show opposite responses, the progressive disease takes precedence.

12.3 Response Criteria for Patients with Solid Tumors

See the table in [Section 8.0](#) for the schedule of tumor evaluations. Eligible patients must have measurable disease present at baseline and have had their disease re-evaluated after at least one dose of protocol therapy. In addition to the scheduled scans, a confirmatory scan should be obtained on the next consecutive cycle following initial documentation of objective response.

As outlined, patients will be assigned to one of the following categories for assessment of response: a) solid tumor (non-CNS) and measurable disease ([Section 12.4](#)); b) neuroblastoma with MIBG positive lesions ([Section 12.5](#)); c) CNS tumor ([Section 12.7](#)); and d) lymphoma/histiocytosis ([Section 12.8](#)). Note: Neuroblastoma patients who do not have MIBG positive lesions should be assessed for response as solid tumor patients with measurable disease.

Response and progression will be evaluated in this study using the revised Response Evaluation Criteria in Solid Tumors (RECIST) guideline (version 1.1).⁴² Key points are that 5 target lesions are identified and that changes in the *largest* diameter (unidimensional measurement) of the tumor lesions but the *shortest* diameter of malignant lymph nodes are used in the RECIST v 1.1 criteria.

12.3.1 Definitions

12.3.1.1 Evaluable for objective response:

Eligible patients who receive at least one dose of protocol therapy will be considered evaluable for response. Evaluable patients who demonstrate a complete or partial response confirmed by central review before receiving non-protocol anti-cancer therapy will be considered a responder. All other evaluable patients will be considered non-responders.

12.3.1.2 Evaluable Non-Target Disease Response:

Eligible patients who have evaluable but not measurable disease and have received at least one dose of protocol therapy will be considered evaluable for non-target disease. The response assessment is based on

the presence, absence, or unequivocal progression of the lesions.

12.3.2 Disease Parameters

12.3.2.1 **Measurable disease:** Measurable lesions are defined as those that can be accurately measured in at least one dimension (longest diameter to be recorded) as ≥ 20 mm by chest x-ray, as ≥ 10 mm with CT scan, or ≥ 10 mm with calipers by clinical exam. All tumor measurements must be recorded in millimeters (or decimal fractions of centimeters).

Note: Tumor lesions that are situated in a previously irradiated area might or might not be considered measurable. If the investigator thinks it appropriate to include them, the conditions under which such lesions should be considered must be defined in the protocol.

12.3.2.2 **Malignant lymph nodes:** To be considered pathologically enlarged and measurable, a lymph node must be ≥ 15 mm in short axis when assessed by CT scan (CT scan slice thickness no greater than 5 mm). At baseline and in follow-up, only the short axis will be measured and followed.

12.3.2.3 **Non-measurable disease:** All other lesions (or sites of disease), including small lesions (longest diameter < 10 mm or pathological lymph nodes with ≥ 10 to < 15 mm short axis), are considered non-measurable disease. Bone lesions, leptomeningeal disease, ascites, pleural/pericardial effusions, lymphangitis cutis/pulmonitis, inflammatory breast disease, and abdominal masses (not followed by CT or MRI), are considered as non-measurable.

Note: Cystic lesions that meet the criteria for radiographically defined simple cysts should not be considered as malignant lesions (neither measurable nor non-measurable) since they are, by definition, simple cysts. 'Cystic lesions' thought to represent cystic metastases can be considered as measurable lesions, if they meet the definition of measurability described above. However, if non-cystic lesions are present in the same patient, these are preferred for selection as target lesions.

12.3.2.4 **Target lesions:** All measurable lesions up to a maximum of 2 lesions per organ and 5 lesions in total, representative of all involved organs, should be identified as target lesions and recorded and measured at baseline. Target lesions should be selected on the basis of their size (lesions with the longest diameter), be representative of all involved organs, but in addition should be those that lend themselves to reproducible repeated measurements. It may be the case that, on occasion, the largest lesion does not lend itself to reproducible measurement in which circumstance the next largest lesion that can be measured reproducibly should be selected. A sum of the diameters (longest for non-nodal lesions, short axis for nodal lesions) for all target lesions will be calculated and reported as the baseline sum diameters. If lymph nodes are to be included in the sum, then only the short axis is added into the sum. The baseline sum diameters will be

used as reference to further characterize any objective tumor regression in the measurable dimension of the disease.

12.3.2.5 **Non-target lesions:** All other lesions (or sites of disease) including any measurable lesions over and above the 5 target lesions should be identified as non-target lesions and should also be recorded at baseline. Measurements of these lesions are not required, but the presence, absence, or in rare cases unequivocal progression of each should be noted throughout follow-up.

12.3.3 **Methods for Evaluation of Measurable Disease**

All measurements should be taken and recorded in metric notation using a ruler or calipers.

The same method of assessment and the same technique should be used to characterize each identified and reported lesion at baseline and during follow-up. Imaging-based evaluation is preferred to evaluation by clinical examination unless the lesion(s) being followed cannot be imaged but are assessable by clinical exam.

12.3.3.1 **Clinical lesions:** Clinical lesions will only be considered measurable when they are superficial (e.g., skin nodules and palpable lymph nodes) and ≥ 10 mm diameter as assessed using calipers (e.g., skin nodules). In the case of skin lesions, documentation by color photography, including a ruler to estimate the size of the lesion, is recommended.

12.3.3.2 **Chest x-ray:** Lesions on chest x-ray are acceptable as measurable lesions when they are clearly defined and surrounded by aerated lung. However, CT is preferable.

12.3.3.3 **Conventional CT and MRI:** This guideline has defined measurability of lesions on CT scan based on the assumption that CT slice thickness is 5 mm or less. If CT scans have slice thickness greater than 5 mm, the minimum size for a measurable lesion should be twice the slice thickness. MRI is also acceptable in certain situations (e.g. for body scans). Ideally, the same type of scanner should be used and the image acquisition protocol should be followed as closely as possible to prior scans.

12.3.3.4 **PET-CT:** At present, the low dose or attenuation correction CT portion of a combined PET-CT is not always of optimal diagnostic CT quality for use with RECIST measurements. However, if the site can document that the CT performed as part of a PET-CT is of identical diagnostic quality to a diagnostic CT (with IV and oral contrast), then the CT portion of the PET-CT can be used for RECIST or International Pediatric non-Hodgkin Lymphoma Response Criteria measurements and can be used interchangeably with conventional CT in accurately measuring cancer lesions over time. Note, however, that the PET portion of the CT introduces additional data which may bias an investigator if it is not routinely or serially performed.

12.3.3.5 **Tumor markers:** Tumor markers alone cannot be used to assess response.

If markers are initially above the upper normal limit, they must normalize for a patient to be considered in complete clinical response.

12.3.3.6 Cytology, Histology: These techniques can be used to differentiate between partial responses (PR) and complete responses (CR) in rare cases (e.g., residual lesions in tumor types, such as germ cell tumors, where known residual benign tumors can remain).

Cytology should be obtained if an effusion appears or worsens during treatment when the measurable tumor has met criteria for response or stable disease.

12.3.3.7 FDG-PET: While FDG-PET response assessments need additional study, it is sometimes reasonable to incorporate the use of FDG-PET scanning to complement CT scanning in assessment of progression (particularly possible 'new' disease). New lesions on the basis of FDG-PET imaging can be identified according to the following algorithm:

- a. Negative FDG-PET at baseline, with a positive FDG-PET at follow-up is a sign of PD based on a new lesion.
- b. No FDG-PET at baseline and a positive FDG-PET at follow-up: If the positive FDG-PET at follow-up corresponds to a new site of disease confirmed by CT, this is PD. If the positive FDG-PET at follow-up is not confirmed as a new site of disease on CT, additional follow-up CT scans are needed to determine if there is truly progression occurring at that site (if so, the date of PD will be the date of the initial abnormal FDG-PET scan). If the positive FDG-PET at follow-up corresponds to a pre-existing site of disease on CT that is not progressing on the basis of the anatomic images, this is not PD.

Note: A 'positive' FDG-PET scan lesion means one that is FDG avid with an uptake greater than twice that of the surrounding tissue on the attenuation corrected image.

For patients with a positive PET scan at diagnosis, PET can be used to follow response in addition to a CT scan using the International Pediatric non-Hodgkin Lymphoma Response Criteria.⁴³

